**Statistical Analysis Plan**

Catalyst Biosciences, Inc. **Protocol # MAA-201**

**Version 2.0**

**Syneos Health #1009647**

## **10.6 INTERIM ANALYSES**

No formal interim PK analysis is planned for the study

## **10.7 DEVIATION FROM ANALYSES PLANNED IN PROTOCOL**

The PD population was added to the analysis populations.

Statistical Analysis Plan

Catalyst Biosciences, Inc. Protocol # MAA-201

Version 2.0

Syneos Health #1009647

## 11 ANALYSIS OF IMMUNOGENICITY

### 11.1 IMMUNOGENICITY SAMPLING SCHEDULE

Antibody response and neutralizing antibodies to MarzAA to FVII, FVIIa, and MarzAA will be measured. The schedule of assessments of immunogenicity will be defined by study part as follows:

Part 1a - screening and pre-dose

Part 1b - pre-dose

Part 2 - Pre-dose on Day 1, 7, 14, 21, 28, and 42, and then every 2 weeks until end of study; 30 days after last dose (end of study) at the 1st dose level in the absence of bleeding events.

Bleeding event - within 6 hours of the spontaneous bleed

Dose escalation post-bleeding - days 14, 28, 42; 30 days after last dose (end of study).

### 11.2 IMMUNOGENICITY ENDPOINTS

Occurrence of antibody formation resulting in a decreased endogenous level of FVII or FVIIa

Occurrence of antibody response to MarzAA

The number and percentage antibody formation resulting in a decreased endogenous level of FVII or FVIIa will be presented using safety population.

### 11.3 PRESENTATION OF IMMUNOGENICITY DATA

The sampling for immunogenicity results will be listed combining all time points throughout the study starting from Screening, Parts 1a and 1b and Part 2 with the results from screening and confirmation assay in binary form (Positive/Negative) with the value of titer for Positive immune response.

The immunogenicity results will be summarized by frequency of ADA positive subjects at each time point for all parts of the study. For the Part 2 of the study the summary will take into account the actual dose level and subject with dose escalation will be summarized separately from the subjects who did not experience bleeding event at the starting dose. The frequency of subjects with dose escalation will be summarized by actual dose and time elapsed from the start of each dose escalation.

Statistical Analysis Plan

Catalyst Biosciences, Inc. Protocol # MAA-201

Version 2.0

Syneos Health #1009647

## 12 SAFETY

Safety analyses will be based on the safety population. No inferential statistics will be performed; only summary statistics will be provided. Missing safety data will not be imputed.

### 12.1 EXTENT OF EXPOSURE

Exposure to study drug (in days) will be calculated for part 2 for each dose level and overall for all dose levels.

Exposure is calculated as below:

Exposure in part 2 for each dose level = cumulative number of actual treatment days for each dose level

Exposure overall in part 2 = cumulative number of actual treatment days of the dosing

### 12.2 TREATMENT COMPLIANCE

Study drug compliance (%) is calculated as  $100 \times (\text{total number of days subject report to take study drug in study part 2} / \text{exposure of study drug (in days) in study part 2})$ .

Compliance will be summarized for each dose level in part 2.

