6.4 STUDY INTERVENTION COMPLIANCE

Reasonable efforts should be made to ensure that study drug administration is administered daily in the morning. However, if an unavoidable disruption of the daily administration occurs and a dose is not administered then the subject should be instructed to continue beginning the following day in the morning.

If the subject misses two or more daily doses, then a spontaneous bleeding event will result in a dose escalation only if it occurs 4 days or longer after resumption of the daily administration.

MAA-201 VERSION 2.0

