9.4.3 Analysis of the Secondary Endpoint(s)

Study drug exposure and compliance will be provided for both phases, and by treatment group for the Treatment Phase.

The following parameters will be documented:

MAA-201 VERSION 2.0

- Occurrence of clinical thrombotic event not attributable to another cause, and occurrence of antibody formation resulting in a decreased endogenous level of FVII or FVIIa.
- Change in coagulation parameters (PT, aPTT, fibrinogen, MarzAA antigen and activity levels, and TGT) from pre-dose.
- Occurrence of an antibody response to MarzAA and whether it is inhibitory and cross-reactive to wt-rFVIIa or wt-FVII.
- Clinically significant levels of thrombogenicity markers resulting from daily SC administration of MarzAA

The frequencies of these events will be summarized as proportions and counts.

Protocol deviations will be listed. All major protocol deviations (in particular those regarding entry criteria) will be summarized in the study report.

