**Version 2.0**

**Syneos Health #1009647**

After the first IV dose of MarzAA, subjects will record daily study drug administration (to assess compliance), injection site assessment, any AEs they may experience, and bleeding episodes (location, inciting event if not spontaneous, and treatment administered), and patient reported outcome (PRO) scales.

Once a subject is enrolled into the trial, the study will be conducted in two phases consisting of three parts (occurring consecutively):

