### 4.2 SECONDARY ENDPOINTS

The secondary endpoints will include:

- Occurrence of breakthrough bleeds requiring escalation to higher dose level.
- Safety parameters: Occurrence of clinical thrombotic event not attributable to another cause, and occurrence of antibody formation resulting in a decreased endogenous level of FVII or FVIIa.
- Change in coagulation parameters (prothrombin time (PT), activated partial thromboplastin time (aPTT), fibrinogen, MarzAA antigen and activity levels, and thrombin generation test (TGT)) from pre-dose.
- Occurrence of an antibody response to MarzAA and whether it is inhibitory and cross-reactive to wt-rFVIIa or wt-FVII.
- Clinically significant levels of thrombogenicity markers resulting from daily SC administration of MarzAA
- Feasibility and ease of use of daily SC self-administration by patient as measured by compliance with treatment
- Breakthrough bleeding events will be categorized as follows:
  - Number of bleeds that are life threatening
  - Number that require hospitalization and/or blood transfusion
  - Number of muscle bleeds

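### The compliance formula in SAP 12.2 divides reported dosing days by actual treatment days, so a missed dose leaves both counts and the measure says nothing about adherence

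*SAP*

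**What the plan says.** SAP 12.2 computes compliance as 100 times the "total number of days subject report to take study drug in study part 2" divided by the "exposure of study drug (in days) in study part 2". It then adds: "Compliance will be summarized for each dose level in part 2".

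The denominator is defined one section earlier. SAP 12.1 states: "Exposure overall in part 2 = cumulative number of actual treatment days of the dosing". It gives a matching definition for each dose level. Neither section uses scheduled, planned or elapsed days.

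Compliance has a specific job. SAP 4.2, like Protocol 9.1, lists as a secondary endpoint "Feasibility and ease of use of daily SC self-administration by patient as measured by compliance with treatment". Protocol 9.4.3 promises the result without a formula: "Study drug exposure and compliance will be provided for both phases, and by treatment group for the Treatment Phase". Protocol 6.4 foresees missed doses and says what the subject should do "if an unavoidable disruption of the daily administration occurs and a dose is not administered".

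**The concern.** Adherence is the share of doses due that were taken. For a ratio to measure it, a missed dose must stay in the denominator when it leaves the numerator. In SAP 12.2 the denominator is itself a count of days on which treatment happened, so a missed dose drops out of both.

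At stake is the only stated summary measure of whether adults with hemophilia and inhibitors can keep up daily self-injection. As written, the report could show compliance at or near 100% whatever the subjects did, and a reader would take that as evidence of feasibility.

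The same section has a second, smaller fault. The formula is written for Part 2 as a whole, but the summary is by dose level. For a subject who escalates, it is not stated that both counts are restricted to the same level.

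**Working it through.** The plan states no compliance figure, so there is nothing to reproduce. The check substitutes SAP 12.1 into SAP 12.2 and compares the result with a due-day ratio.

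**Inputs**
- Numerator: days the subject reports taking drug in Part 2 (SAP 12.2).
- Denominator: cumulative actual treatment days (SAP 12.1).
- Planned length at one dose level: 50 days (Protocol 4.2).
- Longest Part 2 dosing: 197 days (Protocol 1.1 and 4.2).
- Missed doses: assumed values, since the documents give no rate.

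**Formulas**

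Let D be days dosed and M be due days missed.
- SAP 12.2, both counts from one record: 100 × D / D = 100% for any M, provided D > 0.
- Due-day version: 100 × D / (D + M).

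| Due days | Missed | SAP 12.2 | Due-day version |
|---|---|---|---|
| 50 | 1 | 49/49 = 100% | 49/50 = 98.0% |
| 50 | 5 | 45/45 = 100% | 45/50 = 90.0% |
| 50 | 10 | 40/40 = 100% | 40/50 = 80.0% |
| 50 | 25 | 25/25 = 100% | 25/50 = 50.0% |
| 197 | 10 | 187/187 = 100% | 187/197 = 94.9% |
| 197 | 25 | 172/172 = 100% | 172/197 = 87.3% |

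**Two further cases**
- *Extended dosing.* The Protocol 1.1 synopsis allows the study to be lengthened after dosing interruptions. A subject who reaches 50 exposure days over 60 due days scores 50/50 = 100%, against 50/60 = 83.3%. This takes all ten undosed days as missed doses. Undosed days of permitted interruption would not be due days.
- *Stopping without a record of it.* A subject who stops after day 20 of 50, with no documented discontinuation, scores 20/20 = 100%, against 20/50 = 40%. With a documented stop at day 20, both versions give 100%.

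**If the two counts come from different records**
- 50 doses taken but 2 not entered in the diary: 48/50 = 96%, with no dose missed.
- 38 diary days against 40 recorded treatment days: 38/40 = 95.0%.
- 40 diary days against 38 recorded treatment days: 40/38 = 105.3%.

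These values reflect record-keeping. A missed dose that both records show correctly still does not move the ratio.

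**Dose-level mismatch**

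Take a subject with 20 days at one level and 50 at the next. If the whole-Part-2 numerator is set over each level's exposure, the results are 70/20 = 350% and 70/50 = 140%. A programmer would probably not keep that reading, but the text does not exclude it.

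**The case against.** The best defence is that the term actual treatment days is not defined further. It could mean time on treatment at a dose level, taken from start and stop dates. A skipped dose inside that span would then stay in the denominator, and 12.2 would measure something close to adherence. Other parts of the SAP lend this some support: 8.1.1 converts exposure to months on study for the bleeding rate, and 12.2 words its numerator differently from 12.1, as if two different counts were meant.

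The wording is against that reading. Cumulative and actual describe a count of days, not a span. SAP 8.2.1 defines the proportion of bleeding days by counting bleeding days from first to last dose in the numerator, and uses cumulative actual treatment days as a separate term in the denominator. Where the SAP means a span, it says so. The span reading would not rescue the formula either. Undosed days after the last dose would still vanish (20/20 = 100% in the stopping case), while interruptions permitted by Protocol 6.1.2.3 and undosed Day 0 bleed days would count as non-compliance.

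Three other points stand in part:
- **Visibility.** Missed doses can be found in the diary, in vial reconciliation (Protocol 6.2.1) and in the deviation listing (SAP 5.8), and there are only 12 planned subjects. That limits the harm, but a deviation listing is not the compliance summary the protocol promises.
- **Illustrations.** The 40% case needs an undocumented stop, and Protocol 7.2 requires the reason and date of withdrawal to be recorded. The 83.3% case needs all ten days to be missed doses. The plain 40-of-50 case needs no such condition.
- **Data for the repair.** The diary contents listed in Protocol 8.1 and 8.2.4 do not include a reason for a skipped dose, and Protocol 6.1.2.3 leaves interruption for a bleed to judgement. Most reasons should be derivable from bleed onset and resolution dates and from adverse event records, but this should be confirmed.

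**Conclusion.** The point holds. On the wording of SAP 12.1 and 12.2, compliance is 100% for any number of missed doses if one dosing record supplies both counts, and a measure of agreement between records if two do. Neither document gives another formula, so the feasibility endpoint has no informative summary measure as defined.

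The size of the distortion depends on how many doses are missed, which the documents do not say. With 50 due days it is 2 percentage points for one missed dose and 20 for ten. The conclusion rests on reading actual treatment days as days on which drug was taken, which the text supports.

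This should be corrected, but its reach is limited. Compliance is descriptive, does not enter the primary test, and the underlying data are not lost.

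**What to change.** Rewrite the denominator in SAP 12.2 as the number of days on which a dose was due:

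- Count from the first scheduled dose at a dose level to the day before the next level starts. For the last level, count to the scheduled end of treatment, including any extension, or to the documented discontinuation.
- Exclude a day of interruption permitted by Protocol 6.1.2.3, or a Day 0 bleed day, only if no dose was taken that day. The condition matters because dosing is in the morning and can precede a bleed on the same day. With 10 doses on 10 days, the last being a dosed Day 0, removing every Day 0 gives 10/9 = 111%. Removing only undosed ones gives 10/10 = 100%.
- Restrict numerator and denominator to the same dose level for the by-level summary, and give a separate overall Part 2 figure.
- Name the record that supplies the dosing days, and state how an undosed day with no recorded reason is classified.
- Leave exposure in SAP 12.1 as it is. It is the time base for the annualized bleeding rate in SAP 8.1.1, and changing it here would alter the primary analysis.

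The cost is a short rule and slightly more programming to classify each undosed day as permitted or missed. That needs the reason for each interruption as well as its dates. No new visits or samples are needed.

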### 12.3 ADVERSE EVENTS / ADVERSE DRUG REACTIONS

Adverse events will be coded using MedDRA Version 20.1 to classify events under primary SOC and PT.

A treatment emergent adverse event (TEAE) is defined as an AE that either begins after the first dose of study drug in this study or worsens after the first dose of study drug in this study but not later than the date of last dose + 30 days.

TEAEs will be assigned to each study part (part 1 or part 2) if the start date of the TEAE is after the first dosing date/time in part 1 or first date of dosing in part 2 for each dose level. TEAEs will be summarized for part 1 and 2 and different dose levels in part 2.

Number of subjects per TEAE and number of events per TEAE below will be summarized by SOC, PT and by study part/dose level. Multiple occurrences of an AE are counted only once per subject per SOC and PT for summary tables:

- Incidence of all TEAEs
- Incidence of all TEAEs by maximum severity (in the following order: severe, moderate and mild). Missing severity will be considered as severe.

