1. PROTOCOL SUMMARY

1.1 SYNOPSIS

Title of Study: Phase 2 study to evaluate the pharmacokinetics, bioavailability, pharmacodynamics, efficacy and safety of a daily subcutaneous treatment regimen with marzeptacog alfa (activated) for bleeding prophylaxis in adult subjects with hemophilia A and B with an inhibitor

Primary Objective: To evaluate the efficacy and safety of a daily subcutaneous (SC) treatment regimen with MarzAA for bleeding prophylaxis in adult subjects with Hemophilia A and B with an inhibitor.

Secondary Objectives:

- To determine the pharmacokinetics (PK) of SC MarzAA.
- To determine the bioavailability of MarzAA when given via SC.
- To determine the pharmacodynamics (PD) of SC MarzAA.
- To evaluate and compare the levels of thrombogenicity markers following administration of a SC dose of 30 µg /kg MarzAA with the IV dose of 18 µg/kg MarzAA.
- To evaluate for evidence of the development of antibodies to MarzAA, wild type recombinant factor VIIa (wt-rFVIIa), and/or wt-FVII, and to determine if these are neutralizing antibodies.
- To determine the annualized bleeding rate (ABR) during MarzAA treatment compared to the rate of historic on-demand treatments.

Study Population: Twelve male subjects, aged 18 or older, with confirmed diagnosis of severe congenital hemophilia A or B with an inhibitor and history of frequent spontaneous bleeding episodes (historical annualized bleeding rate [ABR] of ≥ 12).

Phase of Development: Phase 2

Description of Sites: Multinational study conducted at up to approximately 10 centers.

Study Duration: Approximately 1 year

Participant Duration: The minimum duration of treatment for each subject is approximately 2 months (if no dose escalation is required) and the maximum duration is approximately 7 months (if three dose escalations are required).

Screening: Up to 4 weeks

Part 1a: 24 hours (single IV dosing and PK/PD/Safety testing)

Part 1b: 48 hours (single SC dosing and PK/PD/safety testing)

Part 2: Up to 197 days of daily SC dosing

Note: Where interruptions to study drug dosing days are observed, study duration may be extended to incorporate full dosing schedule.

Follow-up: Two weeks after last dose for PK/PD/safety follow-up and then approximately and additional 2 weeks follow-up to study completion.

MAA-201 VERSION 2.0

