Subjects must have no spontaneous bleeding for 50 days at any dose level and at least 50 exposure days and 30 days post-treatment follow-up to complete the study. Subjects escalating to 120 µg/kg will continue treatment for 50 exposure days to determine the bleed rate.

Study Methodology

This multi-center, open-label Phase 2 study will evaluate the PK, bioavailability, PD, efficacy and safety of a daily SC treatment regimen with MarzAA for bleeding prophylaxis in adult subjects with hemophilia A and B with an inhibitor. The study will enroll and dose, both intravenously and subcutaneously, a total of 12 adult male subjects with severe congenital hemophilia A or B with an inhibitor, and history of frequent bleeding episodes during the 6 months prior to enrollment, as per the individual's bleeding and treatment records.

At the screening visit and prior to any study procedures, subjects will sign an informed consent form (ICF). Eligibility to participate in the study will be determined by inclusion and exclusion criteria elicited from medical history, hemophilia history, physical examination, laboratory assessments and an electrocardiogram (ECG). At screening, subjects will be provided with a diary in which they will be instructed to record any adverse events (AEs) and concomitant medication. The screening period duration may be up to 4 weeks.

After the first IV dose of MarzAA, subjects will record daily study drug administration (to assess compliance), injection site assessment, any AEs they may experience, and bleeding episodes (location, inciting event if not spontaneous, and treatment administered), and patient reported outcome (PRO) scales.

Once a subject is enrolled into the trial, the study will be conducted in two phases consisting of three parts (occurring consecutively):

Part 1: Single dose administration

Part 1a (24 hours): Single IV administration of MarzAA at 18 µg /kg with assessment of PK, PD, and safety for 24 hours post-dose.

Part 1b (48 hours): Single SC administration of MarzAA at 30 µg /kg with assessment of PK, PD, and safety for 48 hours post-dose

Part 2: Daily SC administration

Daily SC administration of MarzAA at 30 µg /kg with assessment of PK, PD, and safety at designated days for 50 treatment days.

If dose escalation is required because of a spontaneous bleeding episode, then assessments of PK, PD, and safety will be at designated days for an additional 50 treatment days.

MAA-201 VERSION 2.0

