**** Assessments performed on Day 7, 14, 21, 28, 42, and 50 will be done pre-dose, unless otherwise specified.**

- Interim targeted evaluation, per investigator's discretion, as indicated on presentation of subject at study visit and review of diary entries (including PRO scales).
- Clinical Signs of Thrombosis – See Appendix A.**
- Local Laboratory: **Hematology** - CBC and platelet count, CD4, **Chemistry** - Sodium, potassium, chloride, bicarbonate, hepatic enzymes (ALT, AST, GGT), bilirubin, albumin, BUN, creatinine, **Troponin Level**.
- Central Laboratory: **Coagulation assays** - PT, aPTT, fibrinogen, FVII, FVIIa activity, and TGI, **Thrombogenicity markers** - D-dimer, F1+2, and TAT, **Pharmacokinetics** - MarzAA antigen and activity, **Immunogenicity assays** - to FVII, FVIIa, and MarzAA.
- Day 0 PK sampling should occur within 6 hours of spontaneous bleed, if feasible.
- Days 7, 14, 21, 28, 50: Sampling will be done Pre- and Post-dose at 7 hours.
- After Day 42, sampling will be done every two (2) weeks until the End of Study visit.
- PRO scales (**Appendix B**): EQ-5D, VAS; Haem-A-QoL; HAL.
- Subjects must have been at the same dose level for 50 days to complete the study.
- At an Unscheduled Visit, perform only the assessments as appropriate to the reason for the visit.
- End of Study Visit will occur 30 days after the last dose.

MAA-201 VERSION 2.0

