6.1.2.1 Guidelines for Dose Escalation

An escalation to the next dose level is required if a spontaneous bleeding event occurs after the fifth daily dose on a dose level. A dose escalation will not occur if the subject is on the maximum dose level of 120 µg/kg. A spontaneous bleeding episode is defined as one that is precipitated by normal activities of daily living (ADL). Subjects will use their current bypass regimen for any spontaneous or traumatic bleed that occurs while on study drug.

Three dose escalations are allowed during Part 2: 60, 90, and 120 µg/kg (maximum dose).

Safety parameters and PK/PD assessments at each dose level will be monitored to ensure that dose escalation to a higher dose level is appropriate.

The spontaneous bleeding episode must be reported to the clinical team immediately and determination of a dose escalation will be made on review of available clinical information related to the spontaneous bleeding episode and may require subsequent treatment and laboratory data, including available results from the PK/PD/safety assessments.

A decision to proceed with dose escalation will be made by the principal investigator in agreement with personnel who have Sponsor, or designee, medical oversight responsibility.

If there is disagreement amongst any of those individuals, the decision will be reviewed on an urgent basis by an independent Medical Consultant for Safety Oversight.

MAA-201 VERSION 2.0

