#### Part 2: Daily SC administration

At Day 1 of daily SC dosing, subjects will begin their self-administered dosing regimen. MarzAA will be self-administered by subjects daily (at approximately the same time every day), starting with a SC dose of 30 µg/kg MarzAA. At each dose, subjects will record the day and time of the SC injections in their diary. If a spontaneous bleeding episode (defined as one that is precipitated by normal activities of daily living [ADL]) occurs before the fifth daily dose, subjects will continue at the current dosing level. If a spontaneous bleeding episode occurs after the fifth daily dose, the MarzAA dose will be escalated to the next dose level. Three dose escalations are allowed during part 2: 60, 90, and 120 µg/kg (maximum dose). At each dose level escalation, safety and PK/PD will be monitored to ensure that dose escalation to a higher dose level is appropriate. If a subject requires a third dose escalation to the fourth dose level, then they will continue treatment with that dose for 50 days and complete the study, regardless if a spontaneous bleeding episode occurs during the highest treatment dose level.

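### TEAEs are tabulated by Part 2 dose level with no exposure adjustment, although time at a level runs by design from about 5–6 to 50 days, so differences between levels can reflect time at risk alone

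*SAP*

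**What the plan says.** SAP 12.3 sets the TEAE tables: "Number of subjects per TEAE and number of events per TEAE below will be summarized by SOC, PT and by study part/dose level". Every item listed there is an incidence, and none is divided by time. TEAEs count up to 30 days after the last dose. SAP 12.3 does not itself mention percentages; the general rule in SAP 15.2.5.2 (Table Conventions) makes subjects the denominator of any percentage shown. Protocol 9.4.4 speaks of incidence rates but defines no person-time.

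SAP 12.1 derives the quantity that is missing from these tables: "Exposure in part 2 for each dose level = cumulative number of actual treatment days for each dose level". SAP 12.3 does not use it. For efficacy, SAP 8.1.1 does divide bleeds by exposure at the dose level.

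Time at a level is set by the escalation rule in Protocol 6.1.2.1: "An escalation to the next dose level is required if a spontaneous bleeding event occurs after the fifth daily dose on a dose level". Completion requires 50 days at one level: "Subjects must have been at the same dose level for 50 days to complete the study". At the top level bleeding does not shorten the stay: "Subjects escalating to 120 µg/kg will continue treatment for 50 exposure days to determine the bleed rate". SAP 12 describes the whole safety analysis as summary only: "No inferential statistics will be performed; only summary statistics will be provided".

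**The concern.** A level left because of a bleed may hold only a few days of follow-up, while the level where a subject finishes holds 50 treatment days plus the 30-day window. A subject count or percentage at the first covers far less time than at the second, and the table does not show this.

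Safety is part of the primary objective, and Protocol 8.5.7 names thromboembolic events and antibody formation as events of special interest. In a 12-subject study the dose-level TEAE tables are the natural place to look for a pattern by dose. A reader may see a gradient that follow-up time alone has produced, or miss a real one. The problem remains when every event is assigned to the correct level.

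**Working it through.** **Step 1: range of time at a level.** The Protocol synopsis states "Part 2: Up to 197 days of daily SC dosing". Three levels each left just before day 50, then a full fourth level, give 3 × 49 + 50 = 197 days, which matches. A level left because of a bleed thus lasts from about 5–6 days (escalation is possible only after the fifth daily dose) to 49, and the finishing level lasts 50. With identical AE rates, expected events per subject differ by 50/6 = 8.3-fold, or by 80/6 = 13.3-fold once the 30-day window is added to the final level.

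**Step 2: model and assumptions.** The documents give no AE rate. Assume h = 1/50 = 0.02 AEs per day at every level. Assume the same spontaneous bleed rate at every level, ABR = 6, 12 or 18, so r = ABR/365 per day. The value 12 is the plan's null and 6 its planning alternative; 18 extends the range upward. Time at a level below 120 is T = min(5 + X, 50), with X exponential at rate r. The 120 level is 50 days for a completer. Then:

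- chance of leaving a level: q = 1 − exp(−45r)
- mean days at a level: 5 + q/r
- chance of at least one AE at a level: E[1 − exp(−0.02T)]; at 50 days, 1 − exp(−1) = 63%
- expected number of 12 subjects reaching 120: 12q³
- expected events at 30: 12 × mean days × 0.02; at 120: 12q³ × 50 × 0.02

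**Step 3: results on treatment days only.**

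| Bleeds per year | q | Mean days at 30, 60 or 90 | At least one AE at 30, 60 or 90 | At least one AE at 120 | Subjects reaching 120 | Events, 30 vs 120 |
|---|---|---|---|---|---|---|
| 6 | 0.523 | 36.8 | 50% | 63% | 1.7 | 8.8 vs 1.7 |
| 12 | 0.772 | 28.5 | 41% | 63% | 5.5 | 6.8 vs 5.5 |
| 18 | 0.891 | 23.1 | 35% | 63% | 8.5 | 5.5 vs 8.5 |

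The percentage among subjects reaching a level is 1.3 to 1.8 times higher at 120 (63/50 to 63/35) with no dose effect. Event counts run the other way at 6 and 12 bleeds per year, because fewer subjects reach 120.

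**Step 4: adding the 30-day window.** A simulation in whole days, with a shortest stay of 6 days, puts the window on the final level only. At 120 the time at risk becomes 80 days, and 1 − exp(−1.6) = 80%. The percentages at 30 versus 120 are 58% vs 80%, 45% vs 80% and 37% vs 80% at 6, 12 and 18 bleeds per year. Event counts are 12.3 vs 2.8, 8.6 vs 8.8 and 6.4 vs 13.6.

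**Step 5: does a rate remove the artefact?** Divided by time at risk, every level gives 2.0 per 100 subject-days in every scenario. Divided by the SAP 12.1 treatment days while the window's events stay in the numerator, it does not: a subject finishing at 120 has 80 × 0.02 = 1.6 expected events over 50 days, or 3.2 per 100 days. That is a spurious 1.6-fold rise at the final level. Numerator and denominator must cover the same period.

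**The case against.** Safety is descriptive only, so the plan compares nothing formally; it tabulates. That stands. The tables are still laid out by dose level, and columns set side by side will be read against each other.

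A reader might infer that the table as planned will make the top dose look worse. The documents do not support that. SAP 12.3 specifies numbers of subjects and events, and under equal hazards the event count on treatment days at 120 exceeds that at 30 only in the 18-bleed scenario. The inflation applies to percentages among subjects reaching a level, which would enter only through the general table convention.

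The size rests on assumed rates, with bleeding taken as equal at all doses. At the planning value of 6 the percentage contrast is the smallest (50% vs 63%), and fewer than two subjects are expected at 120. Nor is 50 days at 120 guaranteed: Protocol 6.1.2.2, 6.1.2.3 and 7.2 allow de-escalation, interruption and withdrawal, so the figure holds for completers.

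The stated objective concerns a daily SC regimen, and safety at dose is framed around each subject's own optimal dose, not a dose–safety relation. Exposure per level and all AEs are reported, so a reader could form a crude rate by hand. This lowers the stakes, but a crude rate would mismatch the window as in Step 5. Rates would also be imprecise: one event over 1.7 × 50, about 86 subject-days, is 1.2 per 100 days, exact 95% CI 0.03 to 6.5.

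**Conclusion.** The point holds as a gap in the descriptive safety tables. TEAEs are shown by dose level without exposure adjustment, while time at a level varies by design from about 5–6 to 50 days and the 30-day window falls only on the final level. Differences between levels can therefore reflect time at risk alone.

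The direction is not fixed. Percentages among subjects reaching a level are inflated where subjects finish, which is always so for completers at 120 µg/kg, while raw counts can fall with dose and hide a real effect. The mechanism follows from the escalation rule; its size depends on the assumed AE and bleed rates. The change is worth making before database lock, because the plan already derives treatment days per level and already adjusts efficacy for exposure.

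**What to change.** In SAP 12.3, for each Part 2 dose level, add descriptive exposure-adjusted rates for all TEAEs, related TEAEs, serious TEAEs and thrombotic events: events, and subjects with a first event, per 100 subject-days at risk, with exact Poisson 95% CIs. For first events, stop counting a subject's days at that event. Show subject-days in each column header and keep the planned counts.

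Define the period once and use it in both parts of the rate: either on-treatment events over days at that level, or the 30-day window included in both for the final level. This also needs a stated end date for assigning an event to a level, since SAP 12.3 gives only a start.

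State with the tables that the rates are descriptive, are imprecise at sparsely used levels, assume a roughly constant hazard, and do not remove confounding of dose with time on study, bleeding tendency or bypassing-agent use.

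The cost is a few SAP lines and one extra column per table, with no new data collection. The drawback is wide intervals where few subjects contribute.
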